**Ectopy Triggering Ganglionated Plexus Ablation to Prevent
Atrial Fibrillation (GANGLIA-AF)**

ClinicalTrials.gov ID: NCT02487654

Document date: 13th December 2021

STUDY PROTOCOL

GANGLIA-AF (ClinicalTrials.gov identifier NCT02487654) was a prospective, multicenter, randomized, single-blinded clinical study recruiting patients with paroxysmal AF indicated clinically for AF ablation. The recruitment period was between May 2017 and May 2019. Three UK centers participated in the study: Hammersmith Hospital, Imperial College Healthcare NHS Trust, UK; Derriford Hospital, University Hospitals Plymouth NHS Trust, UK; St Bartholomew's Hospital, Barts Health NHS Trust, UK. All patients gave written informed consent, and the study was approved by the local research ethics committee. Patients with symptomatic drug-refractory paroxysmal AF indicated for ablation were recruited to the study. The inclusion and exclusion criteria are included on the ClinicalTrials.gov PRS.

Patients were randomized to PVI or to GPA without PVI. Randomization was performed using a permuted block “sealed envelope” approach. The first block of randomization was performed on 21 consecutive patients, randomized 2:1 to GPA (GPA, n = 14; PVI, n = 7). This was in anticipation for a high rate of crossover from the GPA group as experienced in our previous pilot study.

Afterward, randomization was switched to 1:1 in blocks of 10 for the remainder of the recruitment. Patients and their cardiologists providing their usual care were blinded to their randomization. Operators on the day of ablation, the data collector, and the analyst were unblinded to randomization.

Protocol for all patients

Preoperative work-up

All patients discontinued AADs and β -blockers 5 half-lives before the procedure. Amiodarone was discontinued at least 2 months before the procedure. All patients provided written informed consent for participation in the study, which was approved by the health research authority and the local research ethics committee. Complete blood count, urea and electrolytes, C-reactive protein were measured on the morning before the procedure to ensure suitability for ablation.

Clinical procedures

All patients had general anesthesia. Local policies were followed for anticoagulation and assessment of cardiac thrombus using transesophageal echocardiography. A decapolar catheter was positioned in the coronary sinus. After transseptal puncture, a 20-pole circumferential catheter (LassoNav, Biosense Webster, Diamond Bar, CA) was used to create a respiratory-gated 3-dimensional electroanatomic map of the left atrium (CARTO, Biosense Webster). Blood pressure was continuously monitored using a radial arterial line. Heparin was administered throughout the cases to maintain the activated clotting time of >300 seconds. All data were recorded at 1000 Hz by the electrophysiology recording system (Bard EP, Lowell, MA). At the end of the procedure, heparin was reversed with protamine, and patients were discharged the next morning if well.

GP mapping and ablation

High frequency stimulation (HFS) was performed to locate the left atrial GPs in patients randomized to GPA. A Grass S88 stimulator (Astro-Med, West Warwick, RI) was used to deliver HFS from the distal electrode of a bipolar 3.5-mm irrigated-tip contact force sensing ablation catheter (SmartTouc, Biosense Webster), with a minimum contact force of 3g. A PV catheter was always placed in the nearest PV to the site of HFS testing to capture the earliest PV ectopy signals. Approximately 6 mm spacing was used between each HFS test site to achieve an evenly spaced global left atrial GP map. We did not test for GPs inside the PVs or in the left atrial appendage. We aimed to test up to 80 HFS sites, as this was usually sufficient

to cover all the left atrial surface available for testing as in our previous pilot study. The exact number of HFS sites tested varied between patients, depending on the size of their left atrium and the procedure time.

Two types of HFS techniques were used: “synchronized HFS” to detect ET-GPs and “continuous HFS” to detect AVD-GPs. The synchronized HFS technique was first described by Schauerte et al in canines, who demonstrated that atrial ectopy–triggering response with HFS are abolished with atropine and attenuated with β -blockade, confirming its autonomic mechanism. This was also reproduced in clinical studies.

In this study, for our synchronized HFS protocol, the left atrium was paced at high output (10 V) from the ablation catheter during sinus rhythm (SR) to check for atrial capture and to exclude ventricular capture. Then, we delivered short bursts of HFS trains (10 V, 80 ms duration, 40 Hz) coupled to each paced stimulus to ensure that HFS was delivered within the local atrial refractory period. This stimulated only the nerves and avoided direct myocardial capture. We delivered up to 15 trains of synchronized HFS per test site. If atrial ectopy or AF was triggered, we discontinued pacing and HFS immediately to avoid direct myocardial capture and sustained AF.

Continuous HFS was performed during AF by delivering HFS (10 V, 20 Hz) continuously for up to 10 seconds or until asystole occurred.

The definition for a *positive ET-GP* was reproducible induction of PV or atrial ectopy, AF, or atrial tachycardia (AT). Reproducibility was assessed up to 3 times with HFS. The definition for a *positive AVD-GP* was $\geq 50\%$ increase in the R-R interval during HFS compared with the average 10 R-R intervals before HFS.

The main goal of our study was to map ET-GPs with synchronized HFS during SR. However, if patients developed sustained AF during GP mapping, GPs were ablated until successful restoration of SR. A positive response to GPA during sustained AF was termed “acute AF modulation,” and this was defined as follows: (1) termination to SR, (2) organization to AT, and (3) slowing of AF cycle length by ≥ 30 ms. A subgroup analysis was performed in patients who underwent GPA to correlate long-term freedom from ≥ 30 seconds of AF/AT recurrence. Patients who underwent GPA were divided into those who had (1) $<100\%$ success in acute AF modulation, (2) 100% success in acute AF modulation, and (3) no sustained AF with GP stimulation.

If all GPs were ablated and the patient was still in AF, up to 3 direct current cardioversions were performed to restore SR and to complete GP mapping. If patients remained in incessant AF, AVD-GPs were mapped with continuous HFS and ablated. We targeted AVD-GPs as well in this instance because significant overlap exists with ET-GPs and we wanted to target as many ET-GPs as possible.

¹⁰

After completing GP mapping, all GPs were ablated by delivering a cluster of 3 point-by-point lesions around each GP site, with the contact force of >3 g. Each ablation lesion was for 30 seconds at 30 W except in the posterior wall, where it was limited to 25 W. Catheter irrigation was set to 17 mL/min. This was usually adequate to render any GP negative for any response with repeat HFS testing. All ablated GPs were retested with HFS after ablation. If there was still a positive response, further ablation was performed until no further positive responses could be evoked.

PVI

For patients randomized to the PVI arm, wide antral circumferential ablation was performed around the PVs by using contiguous point-by-point radiofrequency (RF) ablation lesions. The

entry and exit blocks of PVs were confirmed using a PV catheter. Operators used the ablation index to guide PVI on >60% of patients who completed PVI.

Clinical follow-up

Patients were followed up and monitored for 12 months, with continuous remote contact with a clinician. Patients were fitted with 48-hour Holter monitors at 3-, 6-, 9-, 12-month intervals. If patients experienced symptoms between these 3-monthly time points, they were offered further Holter monitors in an attempt to record their symptomatic arrhythmia. Patients with pacemakers, loop recorder devices, and personal AliveCor Kardia electrocardiogram (ECG) (AliveCor Inc, Mountain View, CA) monitoring devices were interrogated throughout their follow-up. Any significant arrhythmia identified on their interrogation counted toward the primary end point regardless of the Holter results. We encouraged patients to discontinue all antiarrhythmic drugs (AADs) following the 3-month blanking period after their ablation procedures, but this was not mandated in the protocol.

Repeat AF ablation

Patients who were randomized to GPA returning for redo AF ablation procedures had repeat HFS testing. This identified any recurrence of GPs or new GPs not previously identified. All GPs identified in the redo procedure were ablated in addition to PVI. Patients who were randomized to PVI returning for redo AF ablation procedures had repeat PVI only.

End point definition

The primary end point was any documented atrial arrhythmia (AF, AT, or atrial flutter) lasting for ≥ 30 seconds consecutively recorded on the Holter monitor, 12-lead ECG, pacemaker, loop recorder, and AliveCor Kardia recorded ECG after a 90-day blanking period.

The secondary end points included repeat ablation for AF/AT/atrial flutter after a 90-day blanking period, mortality, and any significant complications related to the procedure (bleeding, thrombosis, phrenic nerve palsy, and cardiac tamponade) requiring intervention.

Statistics

Data analyses were conducted using the per-protocol (PP) study population. The PP study population excluded patients who were withdrawn after randomization. For sample size calculation, it was estimated that at a statistical power of 80% at a 5% significance level, 108 patients were required to detect 25% difference in primary end point, where 45% in PVI and 20% in GPA are predicted to have recurrent AF/AT. We enrolled 116 patients to allow for ~5% not completing follow-up.

Statistical analysis was performed using SPSS Version 28 (IBM Corporation, Armonk, NY) and Prism 5 (GraphPad, San Diego, CA). Continuous variables were expressed as mean \pm SD. Categorical variables were expressed as number and percentage. D'Agostino and Pearson omnibus and Shapiro-Wilk tests were performed to assess the normality of continuous variables before the comparison of means tests. Mann-Whitney *U* test, Fisher exact test, and unpaired *t* test were used for comparison of means. An event-free survival was estimated using a Kaplan-Meier curve for the primary end point. Clinical parameters associated with AF recurrence and other procedural parameters were studied using univariate and stepwise multivariate analysis in a Cox regression model. All variables with *P* values $\leq .05$ from the univariate analysis and well-established risk factors for AF recurrence, such as age and hypertension, were entered into the multivariate regression analysis. A *P* value of $<.05$ indicated statistical significance.

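### Allocation moved from 2:1 to 1:1 after 21 patients and no analysis by randomization phase is described, so about a tenth of any phase difference common to both arms enters an unstratified comparison (minor)

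*Combined protocol and SAP*

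**What the plan says.** The opening section of the study protocol describes two randomization phases. In the first, "The first block of randomization was performed on 21 consecutive patients, randomized 2:1 to GPA (GPA, n = 14; PVI, n = 7"). The reason given is: "This was in anticipation for a high rate of crossover from the GPA group as experienced in our previous pilot study". In the second, "Afterward, randomization was switched to 1:1 in blocks of 10 for the remainder of the recruitment". The method is permuted blocks with sealed envelopes, and no stratification factor is named. Three centres took part, and "The recruitment period was between May 2017 and May 2019".

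The Statistics section gives 116 enrolled against 108 required, but no final arm totals. It uses a per-protocol population: "The PP study population excluded patients who were withdrawn after randomization". It describes a Kaplan-Meier curve for the primary end point, a list of two-group tests that includes Fisher's exact test, and a Cox model of clinical and procedural parameters. It does not say which test compares the arms on the primary end point. It mentions neither stratification by randomization phase nor adjustment for it.

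**The concern.** The chance of receiving GPA was 2/3 for the first 21 patients and 1/2 for the rest. The arms are comparable by design within each phase, but not when the phases are pooled, because early patients are over-represented in GPA. Chance does not cause this imbalance and larger numbers would not remove it.

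If early and later patients differ in recurrence for a reason that affects both arms, part of that difference is counted as a treatment effect. The mix of centres could change over two years of recruitment. So could the mix of monitoring: devices varied between patients, and "Any significant arrhythmia identified on their interrogation counted toward the primary end point regardless of the Holter results". If early patients did worse in both arms, the bias runs against GPA; if they did better, it favours GPA.

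**Working it through.** **The plan's own figure.** For 45% versus 20%, two-sided 5%, 80% power, pooled variance and no continuity correction:

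n per arm = [1.96 × √(2 × 0.325 × 0.675) + 0.8416 × √(0.45 × 0.55 + 0.20 × 0.80)]² / 0.25² = (1.298 + 0.537)² / 0.0625 = 53.9, so 54 per arm and 108 in total. The stated sample size reproduces, and this point does not affect it.

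**Inputs.** Early phase: 14 GPA and 7 PVI (protocol, opening section). Total: 116 (Statistics). Later phase: 116 − 21 = 95 patients at 1:1. The arm totals below are assumptions.

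**Weight on a shared phase difference** = early share of GPA − early share of PVI.

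| Assumed GPA / PVI totals | Calculation | Weight (points) |
|---|---|---|
| 61.5 / 54.5 (even later split) | 14/61.5 − 7/54.5 | 9.9 |
| 62 / 54 | 14/62 − 7/54 | 9.6 |
| 61 / 55 | 14/61 − 7/55 | 10.2 |
| 58 / 50 (108 analysed) | 14/58 − 7/50 | 10.1 |
| 64 / 52 (last block, one extreme) | 14/64 − 7/52 | 8.4 |
| 59 / 57 (last block, other extreme) | 14/59 − 7/57 | 11.4 |
| 58 / 54 (four early GPA excluded from 62/54) | 10/58 − 7/54 | 4.3 |
| 62 / 52 (two early PVI excluded from 62/54) | 14/62 − 5/52 | 13.0 |

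The last-block range arises because 95 is nine blocks of 10 plus 5 patients.

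**Bias** = weight × shared gap. The gap is not in the documents. Assumed gaps of 10, 20 and 30 points at the even split give 1.0, 2.0 and 3.0 points, or 4%, 8% and 12% of the planned 25. At 61/55 with 32.5% overall recurrence, the standard error is √(0.325 × 0.675 × (1/61 + 1/55)) = 8.7 points, so a 2-point bias is about 0.2 standard errors. At 62/54, a 5-point bias needs a gap of 5/0.096 = 52 points.

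**Error under no treatment effect.** Exact binomial enumeration at 62/54, 61/55 and 58/50, with 35% recurrence in the later phase and 15%, 35%, 45% or 55% in the early phase, each test at two-sided 5%:
- Fisher exact: 3.8% to 4.4%.
- Phase-stratified Mantel-Haenszel: 4.9% to 5.0%.
- Pooled chi-square: 4.8% to 6.1%. With no gap it is already 5.6% at 61/55 and 58/50, so the gap adds at most about 0.5 point.

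**Power for 45% versus 20% with no phase gap.**

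| Totals | Pooled chi-square | Fisher | Stratified |
|---|---|---|---|
| 62 / 54 | 82.1% | 81.5% | 82.5% |
| 61 / 55 | 85.2% | 80.1% | 82.4% |
| 58 / 50 | 82.8% | 76.9% | 79.9% |

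If early rates are 10 points higher in both arms, stratifying gains about 4 points over pooled chi-square at 62/54, but only 0.3 at 61/55 and 0.5 at 58/50.

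**Information kept by stratifying.** (14 × 7/21 + 47.5 × 47.5/95) / (61.5 × 54.5/116) = (4.67 + 23.75)/28.89 = 98.3%.

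**What stratifying does not remove.** Mapping applies to one arm only: "High frequency stimulation (HFS) was performed to locate the left atrial GPs in patients randomized to GPA". Suppose a learning curve gives GPA 55% recurrence early and 35% later, with PVI at 35% throughout. The pooled distortion is 14/62 × 20 = 4.5 points. The stratified one is 4.67/(4.67 + 23.75) × 20 = 3.3 points.

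**The case against.** The strongest reply is that this is a hypothetical. No phase gap is documented, and even a 20-point gap moves the contrast by only about 2 points. The only test for proportions that the Statistics section names, Fisher's, keeps its error below 5% in every scenario computed. The effect with the clearest mechanism, a GPA-only learning curve, is mostly left in place by the remedy. The more basic gap is that no primary between-arm test is specified; phase stratification refines a comparison the plan does not spell out. The calculations above are also for binary outcomes, so the error and power of a stratified log-rank test or Cox model were not computed. All of this stands, and it is why the point is minor. It does not remove the case for a step that costs little and analyses the trial as it was randomized.

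Three stronger readings are tempting, and the documents do not support them.
- A tenth might be taken as an upper limit. It is not: the incomplete last block allows 11.4 points, and losing two early PVI patients would give 13.0.
- The expected GPA crossover might be taken to mean that early GPA patients left the per-protocol set. The documents exclude patients withdrawn after randomization and do not say that crossovers were withdrawn. The 4.3-point figure is an illustration only.
- The 6.1% for pooled chi-square might be read as error inflation caused by the change of ratio. Most of the excess is discreteness, and the plan does not name that test.

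**Conclusion.** The point holds as a minor one. The allocation ratio changed at a known patient and no analysis by phase is described. The early share is therefore about 10 points larger in GPA than in PVI: 8.4 to 11.4 with 116 patients, depending on the last block, and movable either way by per-protocol exclusions. About a tenth of any phase difference shared by both arms passes into an unstratified comparison.

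This rests on assumed arm totals and an assumed gap. Neither the size nor the direction of a gap can be learned from the documents. A reader might infer that the result is biased for or against GPA, or that the conclusion is unsafe; nothing in the documents shows either.

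**What to change.** Stratify the between-arm comparison of the primary end point by randomization phase (the 21 patients of the 2:1 block versus the rest). A stratified log-rank test, a Cox model with treatment as a term and phase as a stratum, or a Mantel-Haenszel risk difference would each do this.

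Recruitment closed in May 2019, the document is dated December 2021, and "Operators on the day of ablation, the data collector, and the analyst were unblinded to randomization". If the primary analysis has already been run, keep it, report the stratified result beside it, and label it as a sensitivity analysis added later.

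State how many of the 14 and 7 early patients remain in the per-protocol set, so that readers can compute the actual weight. Show the treatment difference by phase descriptively, since a GPA-only learning curve would appear there.

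The cost is one stratum term and no new data, but it is not free. About 2% of the information is given up. With no phase gap, power is up to about 3 points below pooled chi-square (85.2% to 82.4% at 61/55, 82.8% to 79.9% at 58/50), part of which reflects that test's 5.6% size at those splits. Against Fisher's test, stratified power is higher by 1.0, 2.3 and 3.0 points at the three splits, partly because Fisher's test is conservative.

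### The arm comparison names no centre or allocation-stage term, although three centres took part and the ratio changed from 2:1 to 1:1

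*Combined protocol and SAP*

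**What the plan says.** On centres and allocation, the Study protocol section states "Three UK centers participated in the study" and "Randomization was performed using a permuted block" scheme with sealed envelopes. It continues: "The first block of randomization was performed on 21 consecutive patients, randomized 2:1 to GPA (GPA, n = 14; PVI, n = 7". After that, "randomization was switched to 1:1 in blocks of 10 for the remainder of the recruitment". It does not say whether there was one list or one per centre, and it does not say where the first 21 patients were treated.

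On analysis, the Statistics section says "An event-free survival was estimated using a Kaplan-Meier curve for the primary end point". It names no test of the two curves. The Cox model it describes is a stepwise search for factors linked to recurrence, with procedural parameters among the candidates. Centre, operator and allocation stage are not named as a stratum or covariate anywhere.

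On delivery, the PVI section reports "Operators used the ablation index to guide PVI on >60% of patients who completed PVI", and the GP mapping and ablation section reports "The exact number of HFS sites tested varied between patients, depending on the size of their left atrium and the procedure time". Neither statement is linked to centre.

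On masking, "Operators on the day of ablation, the data collector, and the analyst were unblinded to randomization".

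**The concern.** Centre is known before allocation and may be related to recurrence through operator, case mix or local practice. A trial of two catheter procedures at three sites would usually balance allocation by centre, adjust for it, or do both. This plan describes neither.

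The change of ratio gives the omission more weight. Pooling patients from a 2:1 stage and a 1:1 stage leaves the arms comparable only if the patients in the two stages are alike. If one centre supplied most of the early patients, it is over-represented in the GPA arm by design rather than by chance. Any difference in recurrence between that centre and the others then shifts the arm estimate systematically. The shift goes against GPA if that centre has higher recurrence, and in its favour if lower. What is at stake is a small error in the estimate and some power.

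**Working it through.** **Inputs from the documents.** Three centres; 21 patients at 14:7, then 1:1; 116 enrolled; recurrence of 45% (PVI) and 20% (GPA); 80% power; 5% significance.

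**Assumptions, because the documents give no figures.** Centre sizes of 70/23/23 or 39/39/38; recurrence differences between centres of up to 30 points.

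**1. The plan's own figure.** Two-sided, no continuity correction, with a mean rate of 0.325:

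n per arm = [1.96·√(2·0.325·0.675) + 0.842·√(0.45·0.55 + 0.20·0.80)]² / 0.25² = 53.9, so 54 per arm and 108 in total. This reproduces the stated 108.

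**2. Expected split and standard error.** GPA: 14 + 95/2 = 61.5. PVI: 7 + 95/2 = 54.5. Standard error of the difference = √(0.45·0.55/54.5 + 0.20·0.80/61.5) = 0.0845, about 8.5 points.

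**3. Chance imbalance if one list ignored centre.** For a centre holding a share p of patients, the SD of the arm difference in that share is √[p(1−p)(1/61.5 + 1/54.5)]:
- p = 20%: 7.4 points
- p = 33%: 8.8 points
- p = 50%: 9.3 points

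With a centre difference of 10 to 30 points, one SD of imbalance moves the estimate by between 7.4 × 0.10 = 0.7 and 9.3 × 0.30 = 2.8 points. The direction is random and the expected shift is zero.

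**4. Same centre mix in both stages (simulation, 4,000 runs per scenario, 116 patients, one list).** The unstratified two-proportion test showed bias within simulation error of zero and type I error of 4.7% to 5.5%. At a 30-point spread between the highest and lowest centre, with the third midway, power was 84.4% unstratified against 86.4% for a centre-stratified Cochran-Mantel-Haenszel (CMH) test with equal centres. With 70/23/23 it was 80.9% against 81.7%. Simulation error on a power figure is about √(0.8·0.2/4000) = 0.6 points.

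**5. All of the first 21 patients from one centre (assumption).** Of that centre's m patients, 14 + (m−21)/2 are expected in GPA and 7 + (m−21)/2 in PVI.
- m = 70: 38.5/61.5 = 62.6% of GPA, against 31.5/54.5 = 57.8% of PVI; gap 4.8 points
- m = 39: 23/61.5 = 37.4% of GPA, against 16/54.5 = 29.4% of PVI; gap 8.0 points

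Bias = gap × difference between that centre and the others. For 10 to 30 points it is 0.5 to 1.4 points (m = 70) or 0.8 to 2.4 points (m = 39).

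The simulated shifts at a 30-point spread were 1.0 to 1.2 and 1.6 to 1.8 points. They are smaller because the third centre lies midway, so the early centre differs from the other two by (15 + 30)/2 = 22.5 points on average: 22.5 × 0.048 = 1.1 and 22.5 × 0.080 = 1.8.

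With the early centre having the highest recurrence and a 30-point spread, power was:
- sizes 70/23/23: 76.7% unstratified, 80.8% CMH
- sizes 39/39/38: 78.4% unstratified, 86.6% CMH

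Bias of the centre-stratified estimate was about zero in every scenario.

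**The case against.** The strongest case against is that the point is small. Allocation that ignores centre, at a constant ratio, is still valid. Chance imbalance is already covered by the standard error of about 8.5 points, so it is not an additional error. Even the extreme case above gives at most 2.4/8.5 = 0.28 of a standard error, and it needs an assumed concentration of early patients and an assumed centre difference. The Cox candidate list is also open, so a centre term is unreported rather than excluded. All of this stands, and it limits the point to a refinement.

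It does not remove the point. The standard error does not cover a shift produced by the change of ratio, and the text gives the reader no means of ruling that shift out.

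A reader might also infer three stronger things that the documents do not support:
- **That allocation was unbalanced by centre.** The text is silent; separate lists by centre after the first 21 patients are not excluded.
- **That variable ablation-index use biases the arm comparison.** It is variation within the PVI arm, just as the number of HFS sites is variation within the GPA arm. Both describe the treatment as delivered. Neither is tied to centre, and stratifying by centre would not remove variation within a centre.
- **That one centre had prior mapping experience, so GPA may have worked only there.** The documents mention an earlier pilot study but do not say which centre ran it or how experienced the others were.

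**Conclusion.** The point holds as a minor one. No balancing by centre is described, and neither centre nor allocation stage is named in the primary comparison. If centre mix was the same in the 2:1 and 1:1 stages, the consequence is chance imbalance and a power loss of at most about 2 points in the scenarios examined. If it differed, there is a systematic shift of about 0.5 to 2.4 points in the extreme case examined, against a target difference of 25 points.

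These sizes rest on assumed centre sizes, assumed centre differences of 10 to 30 points and, for the bias, on all of the first 21 patients coming from one centre. A shift of this size is unlikely to change the conclusion unless the result is near the significance boundary.

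**What to change.** - State whether there was one list or one per centre, and where the first 21 patients were treated.
- Report a table of arm by centre by allocation stage. This alone shows whether the route to bias is open.
- Specify the arm comparison as a log-rank test and a Cox hazard ratio for arm, both stratified by centre and allocation stage. Stratifying by stage compares patients only within a fixed ratio; adding centre deals with chance imbalance. Recruitment ended in May 2019 and the analyst was unblinded, so label it a sensitivity analysis if results are already known.
- Show effects by centre descriptively only. The planned rates imply 54.5 × 0.45 + 61.5 × 0.20 ≈ 37 events, about 12 per centre if the centres are equal, which is too few to judge whether the effect differs between centres.

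The cost is two stratification factors and one table, provided that centre and allocation order were recorded. The downside is a slight loss of information in sparse strata. In the simulations with no centre differences and the same centre mix in both stages, the centre-stratified test had about 1 point less power (82.9% against 84.3% with 70/23/23; 83.0% against 84.1% with equal centres). Crossing centre with stage gives up to six strata, so very small ones should be merged by a written rule that uses stratum size only.

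### The chance of detecting the primary event depends on whether a patient has an implanted device, and neither the randomization nor the described primary analysis accounts for this

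*Combined protocol and SAP*

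**What the plan says.** Clinical follow-up sets one schedule for everyone: "Patients were fitted with 48-hour Holter monitors at 3-, 6-, 9-, 12-month intervals". Patients with symptoms between those points are not left to the schedule: "they were offered further Holter monitors in an attempt to record their symptomatic arrhythmia". A further group is watched more closely: "Patients with pacemakers, loop recorder devices, and personal AliveCor Kardia electrocardiogram (ECG" monitors are interrogated during follow-up, and an arrhythmia found that way is an end point event even if the Holter is clean. End point definition adds the 12-lead ECG to the list of sources and sets the threshold at 30 seconds, after a 90-day blanking period.

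The opening study description gives permuted-block randomization (a first block of 21 at 2:1, then 1:1 in blocks of 10) and names no stratification factor.

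Under Statistics, the primary analysis is described in one sentence: "An event-free survival was estimated using a Kaplan-Meier curve for the primary end point". No between-arm test is attached to that curve, and no stratification, adjustment or sensitivity analysis by monitoring method is described. The Cox models look for parameters associated with recurrence. Variables enter through a univariate P value of .05 or less or as established risk factors, with stepwise selection. Device status is not named.

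**The concern.** With a 30-second threshold, whether a recurrence is seen depends heavily on how long the patient is recorded. A patient with a pacemaker or loop recorder can have a short, silent episode captured on almost any day. A patient without one is recorded continuously for a few scheduled days and otherwise mainly when symptoms prompt it. If the device was in place before randomization, it is a baseline characteristic that strongly predicts whether an event is recorded and is unaffected by the assigned treatment.

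A comparison that ignores such a variable gives up two things. A chance difference in device carriage between arms passes straight into the estimated treatment difference. The variation in detection that the variable could explain also stays in the noise, which costs power in a trial of about 54 per arm designed for 80%.

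**Working it through.** **The plan's own figure.** The inputs from Statistics are "at a statistical power of 80% at a 5% significance level" and "where 45% in PVI and 20% in GPA are predicted to have recurrent AF/AT". Sidedness is not stated; two-sided is assumed. With mean risk (0.45 + 0.20)/2 = 0.325:

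n per arm = [1.96 × √(2 × 0.325 × 0.675) + 0.8416 × √(0.45 × 0.55 + 0.20 × 0.80)]² / 0.25² = (1.298 + 0.537)² / 0.0625 = 53.9, so 54 per arm and 108 in total.

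This matches the plan: "108 patients were required to detect 25% difference in primary end point". It uses one recurrence rate per arm, with no split by monitoring method. The 2:1 first block gives arms of about 57.5 and 50.5 at 108 patients, where power is still 80.1%, so 54 per arm is used below.

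**Scheduled recording time.** Days after blanking: 365 − 90 = 275. Scheduled Holter days: 4 × 2 = 8, and 8/275 = 2.9%. If the 3-month Holter falls inside blanking, 6/275 = 2.2%. These are shares of days, not probabilities of detection, and they cover scheduled recordings only.

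**Assumptions.** The documents do not give the share of patients with an implanted device (s) or the ratio of detection hazards with and without one (h). I take s from 5% to 30% and h as 3 or 4, and hold the overall risks at the planned 45% and 20%.

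**Chance imbalance.** The SD of the between-arm difference in device share is √(2s(1 − s)/54). The third column uses the normal approximation.

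| s | SD (points) | Chance of a gap of 10 points or more | Device carriers among 108 |
|---|---|---|---|
| 5% | 4.2 | 1.7% | about 5 |
| 10% | 5.8 | 8.3% | about 11 |
| 20% | 7.7 | 19.4% | about 22 |
| 30% | 8.8 | 25.7% | about 32 |

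**Effect of a 10-point imbalance.** In each arm, solve (1 − s)(1 − e^(−L)) + s(1 − e^(−hL)) = arm risk for L, the cumulative hazard without a device.

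- s = 20%, h = 3: risks with and without a device are 75.5% and 37.4% in PVI (gap 38.1), and 39.1% and 15.2% in GPA (gap 23.9). The mean gap is 31.0 points, so the shift is 0.10 × 31.0 = 3.1 points.
- s = 30%, h = 4: the gaps are 46.4 and 27.6, mean 37.0, so the shift is 3.7 points.

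Over the whole grid the mean gap runs from about 30 to 42 points, so the shift is about 3 to 4 points.

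**Power.** Log-rank test against device-stratified log-rank test, exponential times to detection, 54 per arm, two-sided 5%, 10,000 simulated trials per row:

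| s | h | Unstratified | Stratified | Gain (points) |
|---|---|---|---|---|
| 5% | 3 | 80.6% | 81.0% | 0.4 |
| 10% | 3 | 80.8% | 82.1% | 1.3 |
| 20% | 3 | 81.6% | 84.5% | 2.9 |
| 30% | 3 | 80.5% | 84.4% | 3.9 |
| 5% | 4 | 80.8% | 81.9% | 1.1 |
| 10% | 4 | 81.8% | 84.9% | 3.2 |
| 20% | 4 | 81.6% | 87.1% | 5.5 |
| 30% | 4 | 81.0% | 87.4% | 6.4 |

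Repeat simulations of the last row gave gains from about 5 to 7 points.

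**A more cautious model.** Treat the outcome as yes/no, with detected recurrence 10 to 30 points higher in device carriers and s from 5% to 30% (40,000 trials per setting). An unadjusted chi-square test has 80% to 81% power. A Mantel-Haenszel test stratified by device has 80% to 84%, a largest gain of about 3 points. With no treatment difference, the rejection rate is 4.4% to 4.7% unadjusted and 4.7% to 5.2% stratified.

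**The case against.** The strongest reply is that nothing is broken. Device status fixed before randomization is independent of arm, the unadjusted test holds its 5% level, and the usual standard error already allows for chance imbalance. That stands: the issue is precision and conditional accuracy, not validity. A reader might infer that the arms are known to differ in device carriage, or that the result is biased. The documents support neither. They do not say how many patients had devices, whether the devices preceded randomization, or how they were distributed between arms. The operators, data collector and analyst were unblinded, but nothing says interrogation differed by arm.

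A second reply is that patients without implants are not confined to 8 days, since symptom-driven Holters, 12-lead ECGs and AliveCor recordings also count. That stands too and narrows the contrast. It does not remove it, because the extra Holters follow symptoms and the documents do not describe the AliveCor device as continuous.

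Third, the size of the gain rests on assumed figures, and at a 5% share it all but vanishes. This is correct, and is why the low end of the range must be shown.

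Fourth, the Cox model could pick up device status. It could, but only if the variable is offered and survives selection, and that model is not described as the primary between-arm comparison.

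**Conclusion.** The point holds as a modest loss of precision. Detection differs between patients by device status, and the described primary analysis makes no use of it. If 5% to 30% carry an implanted device and detection hazard is 3 to 4 times higher in them, stratifying gains about 0 points of power at a 5% share with a ratio of 3, about 1 at 10%, about 3 to 4 at 20% to 30%, and about 5 to 6 at 30% with a ratio of 4. The upper figures need both assumptions to be favourable. The 3-to-4-point shift applies only if a 10-point imbalance occurs, and it may favour either arm.

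It might also be inferred that the planned sample size is wrong. It is not: 108 reproduces exactly, and the remedy does not materially change it.

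**What to change.** Name the primary between-arm comparison, which the plan currently leaves open: a log-rank test, or a Cox model with arm, stratified by implanted pacemaker or loop recorder present before randomization (yes/no). Force the same variable into the multivariable Cox model so that stepwise selection cannot drop it. Use pre-randomization status only, because a device acquired later may reflect outcome or treatment. Report device status by arm.

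The document is dated December 2021, recruitment ended in May 2019, and the analyst was unblinded. If outcome data have already been seen, give the stratified result beside the unadjusted one and label it as added later.

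The cost is a few lines of analysis plan and one variable that should be obtainable from existing records, with no new patients or visits. There are two drawbacks. The hazard ratio becomes conditional on device status. The device stratum may also be small, about 5 to 11 patients at a 5% to 10% share (108 × 0.05 = 5.4; 108 × 0.10 = 10.8), and the gain may then be negligible.
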